1.0 Background

One in five children diagnosed with cancer in the U.S. lives in poverty;¹ and poor children with cancer experience higher risks of relapse and decreased overall survival.^{2,3} We previously found that in the context of a clinical trial, children with acute lymphoblastic leukemia from high-poverty neighborhoods experienced lower 5-year overall survival (85% vs 92%; $p=0.02$) and higher rates of early relapse (92% vs 48%, $p=0.008$) which is more challenging to cure.⁴ Despite these disparities, poverty as a contributor to disease outcome has never been targeted in a systematic fashion in childhood cancer. We hypothesize that interventions targeting modifiable domains of poverty during cancer therapy will reduce disparities in childhood cancer outcomes.

One barrier to the development of poverty-targeted interventions for the clinical setting is the perception of poverty as a non-modifiable variable. Household material hardship (HMH), a concrete measure of poverty defined as unmet basic needs including food, heat, housing or transportation, represents an ideal focus for poverty-targeted intervention. HMH is both associated with inferior child health outcomes and remediable with intervention.⁵⁻⁹ Notably, prior work by our group has identified HMH in 20% of pediatric cancer families at diagnosis and 30% after the initial six months of chemotherapy.¹⁰ Multiple trials in primary care have demonstrated that systematic screening for HMH and referral to existing governmental and community resources (e.g. food stamps or food bank) both reduce HMH and improve health outcomes—including vaccination rates in children, and hypertension and hypercholesterolemia in adults.^{9,11,12} While these data provide proof of principle that poverty-targeted interventions impact health outcomes, we hypothesize that the time-sensitive and life-threatening nature of a childhood cancer diagnosis requires more immediately impactful interventions that build upon systematic screening and referral.

In preliminary qualitative work, we identified food and transportation insecurity as domains of HMH most challenging for pediatric families during cancer therapy. We subsequently developed the Pediatric Cancer Resource Equity (PediCARE) intervention, an HMH-intervention with novel, scalable components targeting food and transportation insecurity with the direct provision of these resources. We refined the PediCARE intervention by pretesting it in a small cohort of newly diagnosed pediatric cancer families with pre-existing HMH (DFCI Protocol 18-275) and gathering qualitative and quantitative parent-feedback on intervention design and conduct. We will now evaluate the feasibility of the refined PediCARE intervention in a pilot randomized trial at two-centers. Data from this feasibility pilot will lay the groundwork for a subsequent multi-center study of PediCARE with a goal of reducing HMH and improving child outcomes.

2.0 Objectives

2.1 Overall Study Objectives:

The overarching goal of this study is to pilot a randomized controlled trial (RCT) of the Pediatric Cancer Resource Equity (PediCARE) intervention to determine feasibility of intervention administration in a childhood cancer population. Secondary goals include generation of effect size estimates for a primary endpoint of reduction in household material hardship (HMH) and a secondary endpoint of Emergency Department and Intensive Care Unit utilization to support

planning of a subsequent definitive multi-center RCT. PediCARE is a poverty-targeted intervention utilizing direct resource provision of groceries and transportation.

2.2 Specific Aims:

Pilot RCT to determine feasibility

To conduct a pilot RCT of the PediCARE intervention in 40 newly diagnosed pediatric cancer families with HMH at DFCI and UAB. Families in the intervention arm will receive PediCARE for 6-months. The control group will receive usual care. Data will be collected by parent survey at baseline and 6-months. The primary outcome will be defined as feasibility. Secondary outcomes will include improvement in HMH scores (range 0-4) at 6-months compared to baseline and Emergency Department (ED) and Intensive Care Unit (ICU) admissions. Analyses will focus on effect size estimates to plan a subsequent RCT.

H2a. Feasibility will be demonstrated by recruitment rate of 75% and follow-up survey data collection of 80% per arm.

H2b: There will be a trend towards a reduction in HMH scores (primary endpoint) and lower proportion of patients experiencing an ED visit or ICU admission over 6-months in the PediCARE versus usual care group.

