4.0 Planned Enrollment

This study aims to enroll a total of 40 participants as follows:

Pilot RCT DFCI and UAB: The target sample size is 40 participants. At DFCI, a total of 28 participants will be enrolled and randomized (thus 14 participants will receive PediCARE and 14 participants will receive UC). At UAB a total of 12 participants will be enrolled and randomized (thus 6 participants will receive PediCARE and 6 participants will receive UC).

Families will be recruited consecutively at each site over a 6-month time period. Patients will be randomized 1:1 to PediCARE versus Usual Care (UC) and randomization will be stratified by site.

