8.0 Study Endpoints

8.1 Feasibility: The primary endpoint of this study is feasibility. Feasibility will be defined as at least 75% consent to randomization and at most 20% attrition per arm. We will assess process barriers to feasibility including recruitment, attrition by arm and parent report of PediCARE component utilization (i.e. food and transportation).

[figure not shown]
Study Timeline (Months)	Months 1 -6 Year 1	Months 7- 12 Year 1	Months 1-6 Year 2
Screen and enroll families (6 months)			
Intervention administration (6 months)			
Data analysis			

8.2 HMM and Utilization: The secondary endpoints of this study will be used to generate effect size estimates to support planning of a subsequent RCT. Secondary endpoints will be evaluated comparing recipients of PediCARE versus Usual Care. Secondary outcomes include change in HMM utilizing an HMM score (range 0-4) at 6-months compared to baseline; and proportion of patients experiencing an Emergency Department (ED) visit or Intensive Care Unit (ICU) admission over 6-months.

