11.0 Statistical Considerations

Accrual: Annually, 420 new patients receive chemotherapy at DFCI and 120 at UAB. Based on prior institutional HMH data, we estimate 20% will be eligible to participate at DFCI (N=84) and 30% will be eligible to participate at UAB (N=36). We estimate a 75% consent rate for a total possible annual sample size of N=90 patients (63 DFCI, 27 UAB). Forty patients will be accrued over 6-months at DFCI (n=28) and UAB (n=12). Patients will be randomized 1:1 by site to PediCARE versus UC.

Analysis Plan: Sample demographic, disease, treatment and utilization variables from the survey instruments and medical chart will be described by summary statistics.

The rate of consent to randomized intervention and the 6-month completion will be estimated along with a 90% confidence interval (CI). Feasibility will be established if the upper bound of the CI contains 75% and 80% for consent and follow-up respectively. With an estimated 60 eligible patients at 6 months, at least 39 (65%; 90% CI 53.6-75.2%) need to enroll for the upper bound of the 90% CI contain 75%. With an estimated 40 randomized patients, at least 28 (70%; 90% CI 56.0-81.7%) need to have complete 6-month data to have the upper bound of the 90% CI contain 80%. The 6-month completion rate will also be estimated along with a 90% CI by randomized arm (PediCARE and UC).

For each family, the difference between 6-month and baseline HMH scores will be categorized as improved (change score <0) or not improved (change score ≥0). For each arm, the proportion of families with improved HMH at the completion of the intervention (6-months) will be estimated along with a 90% exact CI. Based on prior data, we assume a 30% resolution in HMH in UC, thus the 90% CI will be within ±24.9%. For each arm, the per patient number of ED visits and ICU stays will be summarized (median, range). The proportion of patients with at least one ED and/or ICU visit will be estimated for each arm, as well as the difference between arms, along with a 90% confidence interval. Additionally, the rate of HMH at the completion of the intervention pilot (6-months) along with a 90% exact confidence will be estimated for UC and PediCARE. For the PediCARE arm, the cost per patient, study team contact hours, and proportion with successful receipt of all intervention components will be described overall and by site.

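### H2b predicts a trend with no criterion, its effect estimates are meant for planning the RCT, and no between-arm HMH interval is planned to show how imprecise they are at 20 per arm

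*Combined protocol and SAP*

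**What the plan says.** H2b in section 2.2 has two parts. The first is "There will be a trend towards a reduction in HMH scores (primary endpoint"). The second is a "lower proportion of patients experiencing an ED visit or ICU admission over 6-months in the PediCARE versus usual care group". Neither part has a threshold, test or target difference there or in section 11. H2a, by contrast, has numerical criteria for recruitment and follow-up.

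The use of the estimates is stated in two places. Section 2.2: "Analyses will focus on effect size estimates to plan a subsequent RCT". Section 8.2: "The secondary endpoints of this study will be used to generate effect size estimates to support planning of a subsequent RCT". Section 2.1 names HMH reduction as the primary endpoint and ED/ICU use as the secondary endpoint for that planning; in the pilot itself, feasibility is primary.

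On size, section 4.0 says "The target sample size is 40 participants" and "Patients will be randomized 1:1 to PediCARE versus Usual Care (UC) and randomization will be stratified by site". Its site figures (14 + 14 at DFCI, 6 + 6 at UAB) give 20 per arm.

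On analysis, section 11 makes HMH change binary: "the difference between 6-month and baseline HMH scores will be categorized as improved (change score <0) or not improved (change score ≥0"). It then gives each arm's proportion improved, and each arm's HMH rate at 6 months, a 90% exact interval. For ED/ICU it adds the difference between arms with a 90% interval. It has no such line for HMH.

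**The concern.** H2b compares two arms, and as worded a favourable direction is enough to support it. At 20 per arm, direction says little. The size of an observed difference says little more, yet planning the RCT is the one use the plan gives for it.

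Two things are at stake. The report could describe as a trend a difference that chance produces often. And the planners of the RCT would hold an HMH effect estimate, for what appears to be their intended primary endpoint, with no planned interval around the difference and no stated rule for how far to rely on it.

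**Working it through.** **Inputs from the documents.** 20 per arm (4.0). Attrition of up to 20% per arm is tolerated (8.1), so 0.8 × 20 = 16 completers per arm. Assumed UC rate 30% (11.0). Binary HMH improvement and 90% intervals (11.0).

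**Assumptions not in the documents.** True PediCARE rates of 35–70%; a later RCT with two-sided α = 0.05 and 80% power; for step 4, a rule that sizes that RCT on the pilot's observed rates.

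**1. The plan's own figures.** The feasibility intervals reproduce as exact (Clopper–Pearson) 90% CIs: 39/60 gives 53.6–75.2% and 28/40 gives 56.0–81.7%. The ±24.9% that section 11 attaches to the 30% UC rate does not reproduce as a per-arm interval. For 6/20 the exact 90% CI is 14.0–50.8% (−16.0/+20.8 points), and the Wald half-width is 1.645 × √(0.21/20) = 16.9 points. The figure does equal the Wald half-width for a between-arm difference of 30% v 50%, shown in step 3. The documents do not say where it came from.

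**2. Chance of a favourable direction with no true effect.** For two independent Binomial(n, p) arms, P(favourable) = [1 − P(tie)]/2.
- n = 20, p = 0.30: P(tie) = 0.137, so (1 − 0.137)/2 = 43.1%.
- n = 16, p = 0.30: P(tie) = 0.153, so 42.3%.
- n = 20, common rates of 10–50%: 39–44%.
- Comparing mean change scores instead gives about 47–48% (illustrative score distributions).
- At n = 20 and p = 0.30, chance alone gives a gain of at least 10 points 30% of the time and of at least 20 points 11% of the time.
- Both parts of H2b favourable, if independent: 0.431 × 0.431 = 18.6%. With ED/ICU rates of 20–50% the range is 18–19%.

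**3. Precision of the difference.** Half-width = 1.645 × √[p₁(1−p₁)/n + p₂(1−p₂)/n]. At 30% v 50% the numerators sum to 0.21 + 0.25 = 0.46.
- n = 20: 1.645 × √(0.46/20) = 24.9 points, so an observed gain of 20 points runs from about −5 to +45.
- n = 16: 1.645 × √(0.46/16) = 27.9 points.

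**4. Illustration of sizing on the pilot result.** For every favourable pilot outcome at 20 per arm, the RCT size per arm is n = [1.96√(2p̄(1−p̄)) + 0.84√(p₁(1−p₁) + p₂(1−p₂))]²/d², using the observed rates, with p̄ their mean and d their difference. Its power is then evaluated at the true rates and averaged with exact binomial weights.

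One case: the truth is 30% v 50%, which needs 93 per arm. The pilot happens to show 6/20 v 12/20. The formula then gives 42 per arm, and true power is 46%.

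| True gain over 30% (points) | Mean true power | Share of such RCTs below 80% |
|---|---|---|
| 5 | 31% | 86% |
| 10 | 50% | 70% |
| 15 | 61% | 61% |
| 20 | 67% | 56% |
| 25 | 71% | 53% |
| 30 | 73% | 52% |
| 35 | 75% | 48% |
| 40 | 76% | 49% |

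Mean power is below 80% in every row. If UC is instead held at 30% and only the observed difference is used, the shares below 80% for gains of 5 to 30 points are 76%, 63%, 55%, 50%, 47% and 46%. Mean power still stays below 80%.

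**The case against.** The strongest reply is that this is a feasibility pilot with an estimation plan. Section 11 has no efficacy test and no p-value, and it already gives ED/ICU a between-arm difference with its interval. The only pass/fail criteria concern consent and follow-up. On that view the trend is a directional expectation that no analysis uses. This stands as a description of section 11. It does not explain why H2b is worded as a finding to be shown, or why HMH lacks the between-arm interval that ED/ICU has.

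Three stronger readings are tempting, and the documents do not support them.
- A reader might infer that the RCT will be sized on the observed difference, or that the sign of H2b decides whether there is an RCT. The text says only that the estimates support planning. It states no sizing rule and ties no go/no-go decision to H2b, so step 4 shows the consequence of an assumed rule.
- A reader might take 43% as the chance that H2b as a whole is met by luck. H2b joins two endpoints; the joint figure is about 19% if they are independent, and the plan does not say how mixed results would be read.
- A reader might conclude that an RCT sized this way is usually underpowered. That is clear for true gains up to about 15 points, but by 30–40 points it is close to even odds. The sturdier statement is that mean power falls below target.

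It is also fair that choosing a minimum important difference belongs to a later protocol. The pilot need only say that its own point estimate will not take that role.

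**Conclusion.** The point holds as one of wording and of one missing analysis. H2b has no criterion. With no true effect, a favourable direction arises about 43% of the time on each binary endpoint and about 19% on both if independent. An HMH difference of 30% v 50% would carry a 90% interval of about ±25 points, or ±28 with 16 completers per arm, and section 11 does not plan to report that interval. The plan leaves open, without prescribing, reliance on the point estimate. If that were done, mean true power would be about 50–73% instead of 80% for true gains of 10–30 points at 20 per arm.

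The 43% and the interval widths rest on the plan's sample size and on the rates shown. The power figures also rest on the assumed sizing rule, α, target power and true gains. Feasibility, the pilot's primary outcome, is unaffected.

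**What to change.** 1. Section 2.2: reword H2b as estimation. Differences between arms in HMH improvement and in ED/ICU use will be reported with 90% CIs, and no trend or efficacy conclusion will be drawn.
2. Section 11: add the between-arm difference in the proportion with improved HMH, with its 90% CI. In the same edit, reconcile the ±24.9% with the quantity it describes.
3. Sections 2.2 and 8.2: state that the pilot point estimate will not by itself set the RCT effect size, and that the RCT will be sized on a minimum important difference specified in advance. The pilot will inform the UC rate, variability and completion, each with its CI. The UC rate is itself imprecise, as the 14.0–50.8% interval for 6/20 shows.

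The cost is wording in three sections, one added analysis from data already collected, and agreement to specify the minimum important difference before the RCT is sized. No extra families or visits are needed. The downside is that the pilot can no longer claim a trend.

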3.0 Inclusion and Exclusion Criteria

Children diagnosed with cancer at DFCI and UAB will serve as the study cohort for PediCARE with parents/guardians as survey informants and intervention recipients.

3.1 Inclusion criteria:

- 1) Child initiated chemotherapy in the last 2 months for newly diagnosed cancer;
- 2) Planned receipt of at least 4 cycles of chemotherapy at DFCI or UAB;
- 3) Parent/guardian screened positive for HMH*;
- 4) Child is <18 years at time of enrollment

* In accordance with previous research^{15-17,21,42} families will be operationalized as having HMH for eligibility purposes if they report at least one of the below four concrete needs: (1) Food insecurity.^{47,39,48} (2) Housing Insecurity.^{16,17} (3) Energy Insecurity.^{16,17} (4) Transportation Insecurity. Families are considered to have insecurity in a domain if they screen positive to at least one item. HMH screening is performed as standard of care by site-specific providers or will be conducted by a member of the research study team.

3.2 Exclusion criteria:

- 1) Child with diagnosis of relapsed cancer;
- 2) Child planned to receive fewer than 4 cycles of chemotherapy
- 3) Child planned to receive observation, radiation or surgical resection only;
- 4) Planned transfer of child to a non-DFCI or UAB facility for chemotherapy treatment;
- 5) Foreign national family receiving cancer care as an Embassy-pay patient;
- 6) Child is enrolled on DFCI 16-001 (due to ongoing embedded descriptive HMH study) or NA if enrolling at UAB

- 7) Child is enrolled on ANBL1531 or AALL1731 (due to ongoing embedded descriptive HMH studies)

3.3 Inclusion of Women and Minorities:

This study focuses on children with a new diagnosis of cancer with their parents as survey informants and recipients of the PediCARE intervention. This study will enroll racial and ethnic minorities in a manner that is reflective of the proportion of racial and ethnic minorities diagnosed with childhood cancer at each participating site (DFCI and UAB). This study does not focus on any race, ethnicity, or gender. No potential research subjects will be excluded from enrollment based on race, ethnic origin, or gender; nor will any race, ethnicity or gender be preferentially enrolled. All children and their families receiving chemotherapy at DFCI or UAB who meet the primary inclusion criteria of screening positive for household material hardship (HMH) at the time of diagnosis will be considered equally eligible for participation. It is notable that this is a poverty-targeted intervention, and thus based on the epidemiology of poverty in the United States racial and ethnic minorities may well be overrepresented in a cohort selected for pre-existing poverty at the time of diagnosis.

3.4 Inclusion of Children:

This study is a poverty-targeted intervention pilot for pediatric cancer families. Consequently, children diagnosed with cancer at DFCI and UAB will serve as the study cohort for PediCARE with parents/guardians as survey informants and intervention recipients. The rationale for the inclusion of children in this intervention pilot is that our overall research agenda is to improve childhood cancer outcomes utilizing poverty-targeted interventions during therapy. Child involvement in this study will be limited to descriptive medical record abstraction of disease, treatment, and care utilization data. Children will not experience direct study contact or intervention, as such it will represent minimal risk.

4.0 Planned Enrollment

This study aims to enroll a total of 40 participants as follows:

Pilot RCT DFCI and UAB: The target sample size is 40 participants. At DFCI, a total of 28 participants will be enrolled and randomized (thus 14 participants will receive PediCARE and 14 participants will receive UC). At UAB a total of 12 participants will be enrolled and randomized (thus 6 participants will receive PediCARE and 6 participants will receive UC).

Families will be recruited consecutively at each site over a 6-month time period. Patients will be randomized 1:1 to PediCARE versus Usual Care (UC) and randomization will be stratified by site.

5.0 Study-Wide Recruitment Methods

5.1 Recruitment:

New patients at each site (DFCI and UAB) are continuously identified by a local study teams (including clinical providers and trained clinical research assistants (CRAs)) and screened for eligibility to all open research protocols. Study teams will email the primary oncology team for all

PediCARE-eligible patients requesting permission to approach in-line with the standard research practice in Pediatric Oncology. We will reduce gate-keeping effects by educating providers about high family satisfaction with participation in prior HMH studies by our group. The providers will be given the option to inform the study team of non-eligibility by email within 72 hours (see Appendix A). If the 72-hour period elapses with no response, the parent will be considered eligible.

5.2 Consent Process:

Following provider permission, eligible parents/guardians will be approached consecutively by the study team while in clinic or inpatient and offered an opportunity to participate following written informed consent. The study team will offer discussion in a private setting (e.g. consult room) and explain details of the study including study procedures, study risks and benefits and study goals and methods. This will include a discussion of randomization to UC versus PediCARE. The voluntary nature of participation will be highlighted. If, after being introduced to the study and having had the opportunity to ask questions, parent/guardians are willing to participate, they will be asked to sign a written informed consent document.

Dyadic children represent the cohort for analysis, child disease and treatment data will be abstracted from the medical record. Children will experience no direct research contact as a result of participation in the study. Consequently, child assent to participate (medical record abstraction only) will be waived. The justification for this is that parents frequently consider household income/material resource needs to be a sensitive and private topic which they do not wish to share or burden their children with. A requirement to assent children to medical record abstraction will require parental discussion of this topic with children. To this end, parent-participation may be limited were we to require child assent to participation.

Should a child reach the age of majority while enrolled on study, study interventions will continue. Age of majority consent will be waived for these individuals given that patients will experience no direct research contact as a result of participation in the study. Parents/guardians will serve as the survey informants and intervention recipients on behalf of their children, and medical record abstraction does not require patient contact. The justification for this is that parents frequently consider household income/material resource needs to be a sensitive and private topic which they do not wish to share or burden their children with. A requirement to complete age of majority consent would require parental discussion of this topic with children and could limit parent-participation were we to require age of majority consent.

5.3 Registration Process:

All patients, including those enrolled at University of Alabama Birmingham Children's of Alabama (UAB), will be registered in the protocol registration database and assigned a study ID number in the Clinical Trials Management System (CTMS) Oncore.

Registration Process for DFCI:

A member of the study team will confirm eligibility criteria and complete the protocol-specific eligibility checklist.

DF/HCC Standard Operating Procedure for Human Subject Research Titled *Subject Protocol Registration* (SOP #: REGIST-101) must be followed.

Registration Process of UAB:

Eligible patients will be registered on study centrally at the DFCI by the Study Coordinator in real time. Once registration is confirmed, the DFCI study staff facilitating the registration will notify the UAB study staff regarding confirmation of registration. To register a participant, the following documents should be sent to the DFCI Study Coordinator:

- Signed participant consent form
- HIPAA Authorization Form
- Eligibility Checklist

All patients will be randomized to either the PediCARE intervention or Usual Care using the RedCap Database. Each site will be responsible for randomizing their own patients in RedCap.

5.4 Strategies for retention:

We will actively retain families in this study by utilizing ongoing face-to-face study team contact to maintain engagement as well as modest remuneration for ongoing participation. Participants will not be expected to experience any economic burden as part of this study. Enrolled families will receive small (\$50 Amazon gift card) remuneration to off-set the cost of their time participating in baseline and follow-up surveys (total value \$100 if complete both surveys). Prior non-interventional survey-based studies of HMH by our group have demonstrated excellent retention over time.

Due to the relatively low-participant burden, modest remuneration, and patient-centered nature of the intervention we do not anticipate problems with recruitment and retention.

